3. STUDY DESIGN

This is a cluster-randomized controlled trial with FP clinics as the unit of randomization.

4. PROCEDURES

C.2.A. AIM 1: To describe the cervical cancer screening care cascade, from identification of female clients age 21-65 years old, through referral for follow-up of clients with positive or suspicious screens, in FP clinics in Mombasa County. Following characterization of this cascade, we will conduct an analysis of correlates of failure to screen for cervical cancer in FP clients seen over a one-year period.

Study design: This aim will be accomplished by abstracting data from FP registers and interviewing clinic managers. Given the results of the preliminary data presented in C.1.E, any other logs for cervical cancer screening will also be examined to get the most complete and accurate

[figure not shown]

Figure 3. Planned cervical cancer screening care cascade using FP register and other log abstractions

representation of current screening practices. Brief structured interviews with clinic managers will be conducted to understand screening and referral practices in individual FP clinics. Data from FP registers will be merged with clinic-level data from FP clinic manager structured interviews to explore correlates of screening.

Procedures: Cervical cancer screening care cascade: Quantifying the screening care cascade from FP client identification through referrals of positive or suspicious screens will follow a series of steps, illustrated in Figure 4. First, all FP clients 21-65 years of age and recorded at least once during a 3-month period will be identified as a 'cohort' for evaluation over the next 12 months of register data. This step is illustrated taking place retrospectively during the first three months in the figure. Any FP client outside this age range will not be counted as screening is not recommended. The cohort will be followed, using periodic data

[figure not shown]

Figure 4. Family planning register abstraction schema.

abstraction from the register over the next 12 months. The goal will be to identify whether or not cervical cancer screening was completed within 12 months. Among women with completed screens, we will also determine how many were positive (lesions meeting criteria for dysplasia, or other positive test) or suspicious, and how many of these women were referred for care. To supplement these data, any clinic-based cervical cancer screening logs will also be examined for the same time-period as the FP register abstraction. To understand if FP register documentation is capturing screening, this cascade will be compared with the County DHIS reports, which provide individual clinic level data. The level of correlation between these two sources for total FP clients and total screens will be calculated. While we anticipate using FP registers in Aim 2, we may modify this approach, based on quality and correlation of DHIS and FP register data.

Correlates of screening: Data will be abstracted from the FP registers for individual level information (e.g. number of HIV-positive clients, number of FP commodities dispensed). Brief in-person structured interviews with clinic managers (e.g. staff to patient ratio, manager experience, commodities/resources available in clinic, size of population served, urban/periurban/rural, public vs. public/private partnership) will collect clinic-level characteristics from all included clinics and together, these sources will be used to explore individual- and clinic-level correlates of screening that are expected to be generalizable to all FP clinics in Mombasa County.

Data management: Data abstracted from FP registers, other clinic logs, and structured interview data from clinic managers will be aggregated in a REDCap database (49).

C.2.B. AIM 2: To test whether SAIA increases cervical cancer screening compared to usual procedures in a cluster randomized trial in 20 FP clinics in Mombasa County.

Procedures: Quantitative data: Initial information from intervention and control clinics will be obtained from clinic managers. Details about clinic characteristics such as size of the population served and what other services are provided will be collected. Staff characteristics will be collected including the number and type of staff, level of education, and experience of the clinic managers. Cervical cancer screening data will be collected from FP registers including screening method (VIA, visual inspection with Lugol's iodine [VILI], HPV with VILI, HPV alone, Pap smear), clients' HIV status, cervical cancer screening results (positive, negative, suspected), and information on referrals of positive or suspicious screens. These data will be collected at the beginning of the trial during a baseline period before any study procedures are completed, and then periodically every 3 months for all clinics.

Qualitative data: Qualitative IDIs will be conducted with clinic managers to understand cervical cancer screening practices and barriers. Study staff will explain the risks and benefits of participating in the IDIs and the procedures in place to safeguard their opinions. Clinic managers will then be asked to provide written informed consent to participate in an IDI. Types of questions study staff would ask include: "Describe what you know about cervical cancer screening.>"; "In your clinic, what do you think are barriers to screening more women for cervical cancer?"; "What are some ways that cervical cancer screening could be improved in your clinic?". These IDIs will be completed both prior to the trial and during the trial. Questions in the IDIs will be adapted from readily-available CFIR questions to understand where, when, and why the intervention works (50).

Randomization: Restricted randomization will be used to randomize FP clinics into intervention and control arms based on clinic size and location in Mombasa County(51). If facilities differ dramatically in cervical cancer screening rates at baseline, we will also stratify the randomization according to this factor.

Testing SAIA in intervention clinics: Clinics randomized to the intervention arm will be introduced to the five steps of SAIA by study staff (see C.1.B and C.1.D). The cascade analysis will be performed within the FP clinic to identify drop-offs in cervical cancer screening and referrals, using an Excel-based tool adapted from previous SAIA trials. Flow mapping performed by clinic and study staff will describe the cervical cancer screening process including who the client interacts with, timing of these interactions, any cervical cancer screening performed, and any referrals made. Initial drafts will be reviewed together with clinic and study staff to ensure adequate and complete representations of processes. Study staff will work with clinic staff to identify bottlenecks in the process and potential solutions to improve flow. Proposed solutions will be implemented, and the process will be examined again to determine the effect of the implemented changes. The cycle will be repeated approximately every 6-8 weeks during the RCT. Data similar to baseline quantitative data, including numbers of FP clients, number of FP clinic visits, and proportion of FP clients who are screened for cervical cancer, will be abstracted to monitor change in screening over the study period.

Control clinics: Clinics randomized to the control arm will continue usual procedures. Periodic evaluation of cervical cancer screening rates will be examined every 3 months using FP register data.

C.2.C: AIM 3: To determine the cost and budget impact of using SAIA to increase cervical cancer screening in FP clinics in Mombasa County.

Activity Based Micro-Costing Methods: Costs associated with implementing SAIA will be estimated using micro-costing methods to estimate costs for SAIA start-up, personnel required, transportation to and from study clinics, communication costs, consumable materials, and any overhead costs. These cost data will be abstracted from the study budget, clinic expense reports, published labor costs, and interviews with the staff. Data on costs of the SAIA intervention will be collected at both the beginning of the intervention to estimate start-up costs and during the intervention to estimate on-going implementation costs. Costs will be characterized as fixed costs or variable costs that could change over time. We will not include private identifiable information about interviewees.

Time-and-Motion Studies: Time-and-motion studies estimate the time involved in each step of SAIA. These will be estimated over a 2-week period at each intervention site. Multiple SAIA visits will be averaged to give the best estimate of time needed for the intervention. Any time that is for research purposes only, like consent processes, will be subtracted from the total time of the intervention. Multiple providers and clients will be observed to provide a good estimate of the time from clinic entry to clinic exit for a cervical cancer screening. We will not collect private identifiable information about individuals that we will be observing and we will not interact with FP clients or clinic staff while we are doing these observations. The micro-costing and time-and-motion studies will be used to calculate the average cost of a new cervical cancer screen.

Budget Impact Analysis: The budget impact analysis will include direct program costs from the perspective of the DOH, that are estimated from the micro-costing methods illustrated above. Both the 'top-down' approach using routine expense reports and the 'bottom-up' approach using micro-costing will be used to refine our analyses. Standard practices for economic evaluations in health (52) and guidelines from the Panel of Cost-Effectiveness in Health and Medicine (53) will be used where possible to produce results that are accurate and generalizable. A standard 3% discounting rate will be used, with sensitivity analyses that use no discounting and 5% rate. Further sensitivity analyses will be conducted to produce best estimates under varying scenarios.

[figure not shown]

Figure 5. Study Design.

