C.1.D. Adaptations of SAIA methods in ongoing trial, led by [name]. Adaptations of SAIA methods are currently being used to address linkage of HIV services in the ongoing trial “RCT of an implementation science tool to integrate HIV testing into family planning services” (K24 HD088229-01; PI, [name]; FP HIV SAIA Trial) with [name] (primary mentor) and [name] (co-mentor). To meet the national guideline that all women should be tested for HIV when accessing FP services (48), a data entry template for recording of HIV counseling and testing was integrated into the Kenyan FP registers in 2008. Our UW group is addressing this guideline in the FP HIV SAIA trial that compares SAIA to usual procedures to improve HIV testing at FP clinics in Mombasa County. A preliminary performance review of 60 FP clinics in Mombasa County collected data from FP registers and clinic manager interviews. Of 60 clinics, a total of 4389 new FP clients were seen in a 3-month period (mean of 73 new clients per clinic (standard deviation [SD] 81)). Only 23 clinics reported any HIV testing, with a total of 420 new FP clients screened in a 3-month period. Three of these clinics performed the majority of screening (302 screens, 72%). As a Senior Fellow in Infectious Diseases, [name] has led the implementation for this project. She prepared the applications for ethical and humans subjects approval in the US and Kenya, developed data collection tools, trained study staff, created the database, launched the study, and coordinated planning, logistics, and dissemination of findings with Mombasa County. This study has provided [name] with valuable experience in implementing SAIA, and demonstrates the great potential for additional implementation research in Mombasa.

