C.1.E. Preliminary data on cervical cancer screening in Mombasa County from the FP HIV SAIA trial show low screening and incomplete documentation. [name] has had discussions with key collaborators in Mombasa County including the Director of Health (see letter), noting that the majority of cervical cancer screening is conducted in either FP clinics or HIV clinics. The County's policy is that screening should be documented in the FP register. Cervical cancer screening is reported to the County for all clinics that receive County FP commodities. These data are compiled into the District Health Information System (DHIS). The quality of different data sources has not been formally evaluated. Preliminary results from the cervical cancer screening review linked to the FP HIV SAIA trial underscore the importance of the project proposed in the present application. The 60 clinics analyzed saw a mean of 204 FP clients per clinic (SD 172) during a 3-month period (a total of 12,236 clients over the three-month period of our data review). Of the 60 clinics, 4 (7%) did not record cervical cancer screening in the FP register, but reported recording it elsewhere. Because we did not review these alternative records in this initial survey, these clinics are excluded from subsequent analyses. Of the 56 remaining clinics, 7 (13%) recorded any cervical cancer screening. Only 120 women (1%) were screened. These preliminary data suggest few FP clinics perform cervical cancer screening, and that most women accessing FP services are probably not being screened for cervical cancer. Of the clinics offering screening, not all are documenting this activity in the FP register. Moving forward, data collected in outside logs could be entered into FP registers or abstracted separately. These preliminary data provide valuable information for this K08 proposal, which will comprehensively document screening practices in Mombasa County using all the available documentation sources. We will explore why screening prevalence and appropriate documentation is so low, and address this implementation gap with clinic-specific interventions using SAIA.

E. METHODOLOGY

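### Register capture is to be judged by setting a closed, age-limited cohort against DHIS clinic reports not described as limited to those women; the planned correlation would neither expose the mismatch nor measure capture.

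*Combined protocol and SAP*

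**What the plan says.** All references are to the combined protocol and SAP.

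- **Who is in the cascade.** Section E.4 (C.2.A, Aim 1) starts from clients aged 21-65 "recorded at least once during a 3-month period will be identified as a 'cohort' for evaluation over the next 12 months of register data". On age it adds: "Any FP client outside this age range will not be counted as screening is not recommended".
- **What is compared, and why.** Both are in one sentence: "To understand if FP register documentation is capturing screening, this cascade will be compared with the County DHIS reports, which provide individual clinic level data".
- **Statistic named.** "The level of correlation between these two sources for total FP clients and total screens will be calculated". No ratio, capture percentage or threshold is named.
- **What DHIS holds.** Section C.1.E says: "Cervical cancer screening is reported to the County for all clinics that receive County FP commodities". These reports are compiled into DHIS. No limit to a cohort or age range is described, and no calendar period is set for the comparison.
- **What follows from it.** Registers are expected to supply the Aim 2 data, but "we may modify this approach, based on quality and correlation of DHIS and FP register data". Section E.11 (Aim 1 limitations) repeats that the state of documentation will guide the Aim 2 outcome assessment, and notes that the County might accept DHIS reports alone.

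**The concern.** A check of whether one source captures what another reports needs both to count the same people over the same time. Here the register side is fixed at the end of a 3-month window, while the DHIS side, as far as the text goes, keeps taking in new clients. Screens of later entrants sit in one count and are excluded from the other by design. A gap between the totals would therefore mix true under-recording with women who were never eligible for the register count, and nothing in the plan separates the two.

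The comparison informs the choice of data source for the trial's primary outcome. Section E.6 defines that outcome for clients aged 21-65 and excludes women who came solely for screening, who are recognised from their register entries. Clinic-level DHIS totals are not described as supporting either step. An artificial sign of register under-capture, or a high correlation taken as proof of good capture, would be poor evidence for that choice.

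**Working it through.** **Inputs**

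- All FP clients per clinic per quarter, T: 204 (C.1.E). Check: 12,236/60 = 203.9. Section E.5 (Aim 2) gives 183 instead.
- New FP clients per clinic per quarter, N: 73, from C.1.D, where "a total of 4389 new FP clients were seen in a 3-month period" in 60 clinics. Check: 4389/60 = 73.2. Section E.11 gives 60 instead.
- Retention, DHIS period and timing of screening: not given, so these are assumptions. Section E.5 says only that most clients return every 3 months.

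The plan states no capture or shortfall figure, so beyond these means there is nothing to reproduce.

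**Question.** If every screen is recorded, what share of 12 months of clinic screens belongs to women outside the cohort? With matched populations the answer is 0%. Four simple models, with r = 1 - N/T:

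- (a) Head count, every woman equally likely to be screened: 4N/(T + 4N).
- (b) Steady clinic size, screens proportional to attendance in the four follow-up quarters: 1 - mean(r, r², r³, r⁴).
- (c) Full retention, constant screening rate per unit of time: 24N/(12T + 24N).
- (d) As (b), but with the DHIS year starting at the identification quarter: 1 - mean(1, r, r², r³).

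**With T = 204 and N = 73** (r = 131/204 = 0.642)

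- (a) 292/(204 + 292) = 292/496 = 58.9%; the cohort is 204/496 = 41%.
- (b) 1 - (0.642 + 0.412 + 0.265 + 0.170)/4 = 62.8%.
- (c) 1752/(2448 + 1752) = 1752/4200 = 41.7%.
- (d) 1 - (1 + 0.642 + 0.412 + 0.265)/4 = 42.0%.

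**Across the documents' alternative inputs**

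| T, N | (a) | (b) | (c) | (d) |
|---|---|---|---|---|
| 204, 73 | 58.9% | 62.8% | 41.7% | 42.0% |
| 204, 60 | 54.1% | 54.9% | 37.0% | 36.1% |
| 183, 60 | 56.7% | 59.2% | 39.6% | 39.3% |
| 183, 73 | 61.5% | 67.2% | 44.4% | 45.5% |

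The range is 36% to 67%. The age limit, and women who attend only for screening, could widen the gap, but the documents do not allow either to be sized.

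**Effect on the planned correlation.** I simulated 105 clinics, 2,000 times, with perfect recording. Assumptions: lognormal clinic size (mean 204, SD 172); mean screening of 1%, 3% or 8%, varying between clinics; later entrants as in model (a).

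- New-client share equal in all clinics: mean correlation of total screens 0.94, 0.98 and 0.99.
- New-client share varying by clinic (mean 0.36): 0.91, 0.94 and 0.96.
- Shortfall in total screens: 59% throughout.
- Concordance coefficient, which penalises a difference in level: 0.58-0.62.

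A second set used model (b), turnover varying by clinic (mean 0.36), and only 12.5% or 50% of clinics screening. Median correlations were 0.95 and 0.91, with a 5th percentile of about 0.82. The cohort held a median of 40-41% of all screens.

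So the correlation usually stays high while the totals differ by more than half. It tracks whether large clinics are large in both sources, not what fraction of screens the register holds.

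**The case against.** The strongest reply is that the plan may intend whole-register totals. The sentence naming the statistic speaks of total clients and total screens. Section E.2 anticipates including all female clients in the collection windows. Sections E.6 and E.7 list being outside the age range as an exit from the cascade, which implies that such women are counted at its start. The register abstraction figure, which might settle this, is not visible in the text available. This stands as a real ambiguity. Against it, the comparison sentence names the cascade itself, section E.4 says out-of-range clients are not counted, and no separate whole-register tally is described for Aim 1.

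A second reply is that the plan computes only a correlation, which hardly falls. That is right, and it limits the claim: a reader might infer that the plan will report registers missing about 60% of screens, but no capture percentage is planned. The shortfall would appear only if totals were set side by side, which the text permits without specifying. A high correlation is no defence, however, because it does not answer the stated question about capture.

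Third, clinic screening logs for the same period will supplement the registers. They help with missed entries, but do not bring back later clients if they are applied only to the cohort.

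Finally, a reader might infer that this comparison decides the Aim 2 data source and would move the trial off the only source with woman-level data. The documents do not support that. The approach may be modified, on data quality as well as correlation; the results go to the County to find a solution; and clinic logs may also hold woman-level data.

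**Conclusion.** The point holds in a limited form. Followed literally, the comparison sets different groups of women against each other and cannot show whether registers capture screening. Under perfect recording the artificial shortfall in totals is very roughly 36-67%. The 59% head count is one scenario within that range, not a figure from the plan. The range rests on assumed turnover, DHIS period and screening timing, and on the reasonable but unstated reading that DHIS covers all of a clinic's clients. The named correlation would typically be about 0.9 or more, so it would neither reveal the shortfall nor measure capture. If whole-register totals for matched months were intended, the mismatch disappears, but the text needs to say so. The correlation alone would still not measure capture.

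**What to change.** In section E.4 (C.2.A), separate the DHIS comparison from the cohort cascade. State that it uses all register clients and screens, not only the cohort, for the same clinics, calendar months and client group as the DHIS report. Beside the correlation, report the register/DHIS ratio or another agreement measure. Keep the cohort cascade for the 12-month screening outcome and the correlates analysis.

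The cost is a change of wording and a modest extra tally of register entries. Section E.2 already anticipates including all female clients in the collection windows, so little new collection should be needed.

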11. STUDY STRENGTHS/LIMITATIONS

Aim 1 Limitations:

Family planning register use: There are limitations in using program data from FP registers. These registers can have missing information or illegible entries. Also, some FP clinics may be using prior versions of FP registers that lack key information about cervical cancer screening. However, use of routinely collected register data is a main objective of IS and has

the advantage of scalability as new data sources are not required. This aims to keep programmatic costs low, and increase feasibility and scalability. To address issues with FP registers, any clinic-based logs will supplement data in FP registers.

Poor correlation between FP register data and DHIS reports: After discussions with members of the Mombasa County DOH, cervical cancer screening should be documented in both FP registers and DHIS reports. Results of this comparison will be presented to our County collaborators to find a solution for appropriate documentation. The County may decide to provide further guidance in register documentation to all FP clinics, or the County may decide that it is acceptable to use DHIS reports only for cervical cancer screening documentation. The current state of documentation for screening will guide the outcome assessment in Aim 2 (see C.2.B).

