The initial cervical cancer screening care cascade will be presented to Mombasa County. This presentation will inform the County of the current screening activities that may highlight areas for continued important. In addition, comparing the FP registers with DHIS report will provide the County with information about the current state of register documentation. If data quality is not consistent and there is not enough correlation between registers and DHIS reports, it might serve as an impetus for further guidance on appropriate documentation to all FP clinics.

All clinics that could be randomized will have a performance evaluation of cervical cancer screening procedures completed. This evaluation alone is useful quality assurance information for the clinic. Clinics could then act independently to make changes to procedures to increase cervical cancer screening.

Benefits to Subjects in the Intervention Arm of the Trial:

Clinics in the intervention arm will have the benefit of in-depth review of procedures and then SAIA interventions that aims to increase cervical cancer screening. This will benefit individual clinic attendees who may be due for screening **or have never been screened for cervical cancer. Attempts will also be made to make sure that if women are screened by their FP clinics and have an abnormal screen that they are linked with follow-up care.**

The increase in cervical cancer screening and improvement of mechanisms to continue to screen women using SAIA will continue to benefit women and their reproductive health.

7. Importance of knowledge to be gained:

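### The plan checks whether FP registers capture screening by correlating clinic totals with DHIS; a proportional shortfall leaves that correlation near 1, so agreement should be reported and used for the Aim 2 source choice

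*Combined protocol and SAP*

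**What the plan says.** Section E.4 (Procedures, C.2.A, Aim 1) gives the purpose of the comparison: "To understand if FP register documentation is capturing screening, this cascade will be compared with the County DHIS reports". The statistic follows: "The level of correlation between these two sources for total FP clients and total screens will be calculated". The same paragraph expects Aim 2 to use FP registers but adds that "we may modify this approach, based on quality and correlation of DHIS and FP register data".

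Section E.11 (Aim 1 limitations) repeats the link to the trial outcome: "The current state of documentation for screening will guide the outcome assessment in Aim 2". It also allows that "the County may decide that it is acceptable to use DHIS reports only for cervical cancer screening documentation". The Potential Benefits item of section I uses the same criterion: "If data quality is not consistent and there is not enough correlation between registers and DHIS reports".

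No coefficient type, cut-off, ratio, difference or limits of agreement is given, and quality has no stated method. Sections E.4 and E.11 say that clinic screening logs will supplement the registers, but plan no measure of how complete the register is against those logs.

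Section C.1.E already reports a recording problem: "Of the clinics offering screening, not all are documenting this activity in the FP register". Four of 60 clinics kept screening records outside the register. The same section says that the quality of the data sources has not been formally evaluated.

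**The concern.** The question is about completeness: what share of screens reaches the register? Correlation answers a different one: do clinics with more screens in one source also have more in the other? A register missing half of all screens in every clinic ranks and spaces the clinics just as a complete one would.

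What is at stake is the instrument for the Aim 2 primary outcome, the proportion of eligible FP clients screened. A reassuring correlation could help keep a source that understates screening in both arms. It would also leave a capture gap unseen before the trial, and later changes in recording would then be hard to tell apart from changes in screening.

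**Working it through.** **The plan's nearest figure.** The documents give no value for the correlation. The nearest figure is the Aim 2 power in section E.5: 90% with 10 clinics per arm, 8% versus 20%, m = 183 clients per clinic, κ = 0.5. The Hayes-Bennett formula, with two-sided alpha 0.05 assumed, is

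c = 1 + (z₀.₉₇₅ + z₀.₉₀)² × [p₀(1−p₀)/m + p₁(1−p₁)/m + κ²(p₀² + p₁²)] / (p₁−p₀)²

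- Bracket: 0.0736/183 + 0.16/183 + 0.25 × (0.0064 + 0.04) = 0.01288.
- c = 1 + 10.51 × 0.01288 / 0.0144 = 10.4 clinics per arm.
- Power at 10 clinics is 88.7% with the added cluster and 91.7% without it, so the 90% reproduces. It is context here and is not disputed.

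**Algebra.** Let D be the DHIS screens in a clinic and cD the register screens, with c > 0. Then corr(D, cD) = c·Var(D) / [SD(D) × c·SD(D)] = 1. This holds for c = 0.5, 0.25 or 0.10.

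**Simulation 1: all clinics screen.** Inputs were 105 clinics (E.5), clinic size with mean 204 and SD 172 (C.1.E) drawn from a gamma distribution, and mean screening of 8% (E.5) with a between-clinic coefficient of variation of 0.5. Register count was binomial(DHIS count, capture), over 2,000 runs. The capture fractions are assumptions, since the documents give none.

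| Capture | Pearson r | Spearman | Lin's concordance | Register/DHIS ratio |
|---|---|---|---|---|
| 100% | 1.00 | 1.00 | 1.00 | 1.00 |
| 75% | 0.99 | 0.98 | 0.92 | 0.75 |
| 50% | 0.97 | 0.96 | 0.67 | 0.50 |
| 25% | 0.93 | 0.89 | 0.32 | 0.25 |

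At 3% mean screening and 50% capture, r is 0.94 and concordance is 0.67.

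**Simulation 2: few clinics screen.** Here 13% of clinics screen, as in the preliminary register data, with an assumed average share of 23% in those clinics (0.13 × 0.23 = 3.0% overall, the figure used for Aim 1 in E.5). Median Pearson r was:

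- 30% capture: 0.99 if uniform, about 0.96 with capture SD 0.1, about 0.88 with SD 0.2.
- 50% capture: 0.95 to 1.00 across the same three patterns.
- 90% capture: 0.99 to 1.00.

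So r barely separates 50% from 90% capture. The ratio separates them directly.

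**All-or-none recording.** With the same set-up, but each clinic recording either everything or nothing in the register, median r was 0.46 to 0.48 at 30% capture, 0.68 to 0.70 at 50%, and 0.81 to 0.82 at 64%. The 64% is 7/(7 + 4): the clinics with screens in the register, over those plus the four recording elsewhere, assuming that those four do screen.

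**Shared clinic size.** With unrelated screening rates in the two sources but common clinic sizes (mean rate 8%), totals correlated at about 0.60 and rates at about 0.00.

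**Consequence for Aim 2.** With 50% capture in both arms, 8% versus 20% is recorded as 4% versus 10%. The 12-point difference becomes 6 points, and power by the formula above is 85%, against 88.7%.

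**The case against.** The strongest reply is that the plan sets no test for the register to pass. The source choice rests on quality as well as correlation, no cut-off is stated, and section E.11 speaks more broadly of the state of documentation. That is right: a reader might infer that a high r would by itself keep the register, and the text does not say so. What stands is that correlation is the only one of these criteria with a method attached.

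A second reply is that correlation does respond to the recording failure closest to the one documented. Four of 60 clinics recorded screening elsewhere, which resembles all-or-none capture, and r falls under that pattern. So it would be wrong to say that correlation cannot detect under-recording. The blind spot is a uniform or near-uniform shortfall.

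Third, logs supplement the register, so some missing screens are recovered before the comparison with DHIS. This stands as mitigation, but it does not measure what the register alone misses.

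Two further inferences are tempting and unsupported. One is that shared zeros inflate r. "Of the 56 remaining clinics, 7 (13%) recorded any cervical cancer screening" leaves 56 − 7 = 49 clinics with none, but that count comes from FP registers only, and no DHIS equivalent is given. The other is that a better Aim 1 statistic would protect the trial from recording that improves only in intervention clinics. If capture were 50% in control and 100% in intervention clinics, with true screening 8% in both, the register would show 4% versus 8% and a significant result about 65% of the time. That arises during the trial, and an Aim 1 check would not prevent it. Moving to DHIS might not either, as DHIS is compiled from clinic reports.

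**Conclusion.** The point holds in a limited form. The plan asks a completeness question and names a statistic that is blind to a proportional shortfall and inflated by shared clinic size. At 50% capture, with capture SD up to 0.2, r would be about 0.95 to 1.00; under all-or-none recording it would fall to about 0.5 to 0.8 at 30% to 64% capture. These values rest on assumed capture fractions and patterns, an assumed 23% screening share in screening clinics, and gamma clinic sizes.

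The finding does not show that the registers are incomplete to any given degree, that r alone decides the source, or that the trial is invalid. Equal under-capture in both arms costs little power in the worked example, though it halves the apparent difference. If an absolute-agreement coefficient was meant, the shortfall would show, but the plan does not say so. This is worth correcting because the choice of primary-outcome source draws on the result and the better analysis needs no new data source.

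**What to change.** In section E.4 (C.2.A), replace the correlation sentence, or add to it, as follows:

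- Report the ratio of register to DHIS, and of register plus logs to DHIS, for screens and for clients. Give it per clinic with its distribution, and pooled with a confidence interval computed at clinic level.
- Give a Bland-Altman summary of screens among clinics with at least one screen in either source.
- Report register completeness against clinic logs. DHIS is not a validated reference, so a register/DHIS ratio measures agreement and not true capture, and screens absent from both sources stay invisible.
- Base the Aim 2 source choice on these measures under a stated rule, fixed before randomization and applied identically in both arms. Align section E.11 and the Potential Benefits item of section I with it.

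If the source has already been chosen, which the documents do not settle, the same measures should still be reported so that the Aim 2 proportions can be interpreted.

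The cost is a few sentences and slightly more analysis on data already planned. The reported figure will probably look less favourable than a correlation near 1.
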